8.1 Specification of Safety Parameters

8.1.1 Definition of Adverse Events (AE)

An *adverse event* (AE) is any symptom, sign, illness or experience that develops or worsens in severity during the course of the study. Intercurrent illnesses or injuries should be regarded as adverse events. Abnormal results of diagnostic procedures are considered to be adverse events if the abnormality:

- results in study withdrawal
- is associated with a serious adverse event
- is associated with clinical signs or symptoms
- leads to additional treatment or to further diagnostic tests
- is considered by the investigator to be of clinical significance

8.1.2 Definition of Serious Adverse Events (SAE)

Serious Adverse Event

Adverse events are classified as serious or non-serious. A *serious adverse event* is any AE that is:

- fatal
- life-threatening
- requires or prolongs hospital stay
- results in persistent or significant disability or incapacity
- a congenital anomaly or birth defect
- an important medical event

Important medical events are those that may not be immediately life threatening, but are clearly of major clinical significance. They may jeopardize the subject, and may require intervention to prevent one of the other serious outcomes noted above. For example, drug overdose or abuse, a

CONFIDENTIAL

This material is the property of the NYU School of Medicine and Langone Medical Center. Do not disclose or use except as authorized in writing by the study sponsor
Interventional Template Version: 11 January 2019

seizure that did not result in in-patient hospitalization, or intensive treatment of bronchospasm in an emergency department would typically be considered serious.

All adverse events that do not meet any of the criteria for serious should be regarded as ***non-serious adverse events***.

8.1.3 Definition of Unanticipated Problems (UP)

Unanticipated Problems Involving Risk to Subjects or Others

Any incident, experience, or outcome that meets all of the following criteria:

- Unexpected in nature, severity, or frequency (i.e. not described in study-related documents such as the IRB-approved protocol or consent form, the investigators brochure, etc)
- Related or possibly related to participation in the research (i.e. possibly related means there is a reasonable possibility that the incident experience, or outcome may have been caused by the procedures involved in the research)
- Suggests that the research places subjects or others at greater risk of harm (including physical, psychological, economic, or social harm).

This definition could include an unanticipated adverse device effect, any serious adverse effect on health or safety or any life-threatening problem or death caused by, or associated with, a device, if that effect, problem, or death was not previously identified in nature, severity, or degree of incidence in the investigational plan or application (including a supplementary plan or application), or any other unanticipated serious problem associated with a device that relates to the rights, safety, or welfare of subjects (21 CFR 812.3(s)).

8.2 Classification of an Adverse Event

8.2.1 Severity of Event

For AEs not included in the protocol defined grading system, the following guidelines will be used to describe severity.

- **Mild** – Events require minimal or no treatment and do not interfere with the participant's daily activities.
- **Moderate** – Events result in a low level of inconvenience or concern with the therapeutic measures. Moderate events may cause some interference with functioning.
- **Severe** – Events interrupt a participant's usual daily activity and may require systemic drug therapy or other treatment. Severe events are usually potentially life-threatening or incapacitating.

8.2.2 Relationship to Study Agent

For all collected AEs, the clinician who examines and evaluates the participant will determine the AE's causality based on temporal relationship and his/her clinical judgment. The degree of certainty about causality will be graded using the categories below.

- **Definitely Related** – *There is clear evidence to suggest a causal relationship, and other possible contributing factors can be ruled out. The clinical event, including an abnormal laboratory test result, occurs in a plausible time relationship to drug administration and cannot be explained by concurrent disease or other drugs or chemicals. The response to withdrawal of the drug (dechallenge) should be clinically plausible. The event must be pharmacologically or phenomenologically definitive, with use of a satisfactory rechallenge procedure if necessary.*

CONFIDENTIAL

This material is the property of the NYU School of Medicine and Langone Medical Center. Do not disclose or use except as authorized in writing by the study sponsor
Interventional Template Version: 11 January 2019

- **Probably Related** – *There is evidence to suggest a causal relationship, and the influence of other factors is unlikely. The clinical event, including an abnormal laboratory test result, occurs within a reasonable time after administration of the drug, is unlikely to be attributed to concurrent disease or other drugs or chemicals, and follows a clinically reasonable response on withdrawal (dechallenge). Rechallenge information is not required to fulfill this definition.*
- **Possibly Related** – *There is some evidence to suggest a causal relationship (e.g., the event occurred within a reasonable time after administration of the trial medication). However, other factors may have contributed to the event (e.g., the participant's clinical condition, other concomitant events). Although an AE may rate only as "possibly related" soon after discovery, it can be flagged as requiring more information and later be upgraded to "probably related" or "definitely related," as appropriate.*
- **Unlikely to be related** – *A clinical event, including an abnormal laboratory test result, whose temporal relationship to drug administration makes a causal relationship improbable (e.g., the event did not occur within a reasonable time after administration of the trial medication) and in which other drugs or chemicals or underlying disease provides plausible explanations (e.g., the participant's clinical condition, other concomitant treatments).*
- **Not Related** – *The AE is completely independent of study drug administration, and/or evidence exists that the event is definitely related to another etiology. There must be an alternative, definitive etiology documented by the clinician.*

8.2.3 Expectedness

[name] will be responsible for determining whether an AE is expected or unexpected. An AE will be considered unexpected if the nature, severity, or frequency of the event is not consistent with the risk information previously described for the study agent.

8.3 Time Period and Frequency for Event Assessment and Follow-Up

The occurrence of an AE or SAE may come to the attention of study personnel during study visits and interviews of a study participant presenting for medical care, or upon review by a study monitor. All AEs including local and systemic reactions not meeting the criteria for SAEs will be captured on the appropriate RF. Information to be collected includes event description, time of onset, clinician's assessment of severity, relationship to study product (assessed only by those with the training and authority to make a diagnosis), and time of resolution/stabilization of the event. All AEs occurring while on study must be documented appropriately regardless of relationship. All AEs will be followed to adequate resolution.

Any medical condition that is present at the time that the participant is screened will be considered as baseline and not reported as an AE. However, if the study participant's condition deteriorates at any time during the study, it will be recorded as an AE. UPs will be recorded in the data collection system throughout the study.

Changes in the severity of an AE will be documented to allow an assessment of the duration of the event at each level of severity to be performed. AEs characterized as intermittent require documentation of onset and duration of each episode.

The PI will record all reportable events with start dates occurring any time after informed consent is obtained until 7 (for non-serious AEs) or 30 days (for SAEs) after the last day of study participation. At each study visit, the investigator will inquire about the occurrence of AE/SAEs since the last visit. Events will be followed for outcome information until resolution or stabilization.

CONFIDENTIAL

This material is the property of the NYU School of Medicine and Langone Medical Center. Do not disclose or use except as authorized in writing by the study sponsor
Interventional Template Version: 11 January 2019

All unresolved adverse events should be followed by the investigator until the events are resolved, the subject is lost to follow-up, or the adverse event is otherwise explained. At the last scheduled visit, the investigator should instruct each subject to report any subsequent event(s) that the subject, or the subject's personal physician, believes might reasonably be related to participation in this study. The investigator should notify the study sponsor of any death or adverse event occurring at any time after a subject has discontinued or terminated study participation that may reasonably be related to this study. The sponsor should also be notified if the investigator should become aware of the development of cancer or of a congenital anomaly in a subsequently conceived offspring of a subject that has participated in this study.

8.4 Reporting Procedures – Notifying the IRB

8.4.1 Adverse Event Reporting

The patient will be given [name], [name], and [name] contact to report any AE. AE's deemed to be related to the study will be reported to the IRB within 7 days of the investigator becoming aware of the event. [name], the principal investigator, will be responsible for completing and signing off on AE reports.

8.4.2 Serious Adverse Event Reporting

The patient will be given [name], [name], [name] contact to report any SAE. SAE deemed to be related to the study will be reported to the IRB within 3 days of the investigator becoming aware of the event. [name], the principal investigator, will be responsible for completing and signing off on SAE reports.

8.4.3 Unanticipated Problem Reporting

Incidents or events that meet the OHRP criteria for UPs require the creation and completion of an UP report form. It is the site investigator's responsibility to report UPs to their IRB. The UP report will include the following information:

- Protocol identifying information: protocol title and number, PI's name, and the IRB project number;
- A detailed description of the event, incident, experience, or outcome;
- An explanation of the basis for determining that the event, incident, experience, or outcome represents an UP;
- A description of any changes to the protocol or other corrective actions that have been taken or are proposed in response to the UP.

To satisfy the requirement for prompt reporting, UPs will be reported using the following timeline:

- UPs that are SAEs will be reported to the IRB within 3 days of the investigator becoming aware of the event.
- Any other UP will be reported to the IRB within 7 days of the investigator becoming aware of the problem.
- All UPs should be reported to appropriate institutional officials (as required by an institution's written reporting procedures), the supporting agency head (or designee), and OHRP within 7 days of the IR's receipt of the report of the problem from the investigator.

CONFIDENTIAL

This material is the property of the NYU School of Medicine and Langone Medical Center. Do not disclose or use except as authorized in writing by the study sponsor
Interventional Template Version: 11 January 2019

8.4.4 Reporting of Pregnancy

This study is being conducted in post-menopausal women. But in the rare circumstance that a patient becomes pregnant while in this study, the treatment (either arm) will be discontinued, follow-up visit will be scheduled to assess for safety, and a request will be made to follow the patient through her pregnancy to the pregnancy outcome.

8.5 Reporting Procedures – Notifying the Study Sponsor

The study clinician will complete a SAE Form within the following timelines:

- All deaths and immediately life-threatening events, whether related or unrelated, will be recorded on the SAE Form and submitted within 24 hours of site awareness. See Section 1, Key Roles for contact information.
- Other SAEs regardless of relationship will be submitted within 72 hours of site awareness.

All SAEs will be followed until satisfactory resolution or until the investigator deems the event to be chronic or the adherence to be stable.

As a follow-up to the initial report, within the following 48 hours of awareness of the event, the investigator shall provide further information, as applicable, on the unanticipated event or the unanticipated problem in the form of a written narrative. This should include a copy of the completed Unanticipated Problem form, and any other diagnostic information that will assist the understanding of the event. Significant new information on ongoing unanticipated adverse effects shall be provided promptly to the study sponsor.

The study investigator shall complete an Unanticipated Adverse Device Effect Form and submit to the study sponsor and to the reviewing IRB as soon as possible, but in no event later than 10 working days after the investigator first learns of the effect. The study sponsor contact information is provided in Section 1, Key Roles.

As a follow-up to the initial report, within the following 48 hours of awareness of the event, the investigator shall provide further information, as applicable, on the unanticipated event or the unanticipated problem in the form of a written narrative. This should include a copy of the completed Unanticipated Problem form, and any other diagnostic information that will assist the understanding of the event. Significant new information on ongoing unanticipated adverse effects shall be provided promptly to the study sponsor.

The study sponsor is responsible for conducting an evaluation of an unanticipated adverse device effect and shall report the results of such evaluation to FDA and to all reviewing IRBs and participating investigators within 10 working days after the sponsor first receives notice of the effect. Thereafter the sponsor shall submit such additional reports concerning the effect as FDA requests.

8.6 Study Halting Rules

Administration of study agent will be halted when three grade 3 AEs determined to be “probably related” are reported to the PI. There are no predicted grade 3 AE’s for either study agent. The PI will inform the FDA of the temporary halt and the disposition of the study.

CONFIDENTIAL

This material is the property of the NYU School of Medicine and Langone Medical Center. Do not disclose or use except as authorized in writing by the study sponsor
Interventional Template Version: 11 January 2019

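### The halting rule in section 8.6 counts only events judged 'probably related', so as written it leaves out the stronger 'Definitely Related' category of section 8.2.2

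*Combined protocol and SAP*

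**What the plan says.** Section 8.6 (Study Halting Rules) opens with "Administration of study agent will be halted when three grade 3 AEs determined to be" followed by the single label 'probably related', which the protocol itself sets in quotation marks. The trigger is met once these events have been reported to the principal investigator, who then informs the FDA. The section adds "There are no predicted grade 3" events for either agent.

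Section 8.2.2 (Relationship to Study Agent) supplies the causality scale: "The degree of certainty about causality will be graded using the categories below". Five categories follow: Definitely, Probably, Possibly, Unlikely and Not Related. The top one is described as "There is clear evidence to suggest a causal relationship, and other possible contributing factors can be ruled out".

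Section 8.2.1 (Severity of Event) supplies the severity scale: Mild, Moderate and Severe, without numbers. It is introduced by "For AEs not included in the protocol defined grading system, the following guidelines will be used to describe severity". Severe is described in part as "Events interrupt a participant's usual daily activity and may require systemic drug therapy or other treatment".

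**The concern.** A halting rule should be met at least as easily by events with a clear causal link as by events with a probable one. Section 8.6 uses one defined label from an ordered scale and says nothing about the label above it. An investigator who applies the sentence exactly as it stands could record three severe, definitely related events and conclude that the rule had not been met.

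This matters because 8.6 is the only place where the protocol commits to stopping administration at a stated count. Section 10.4.5.1 rules out statistical rules for halting enrolment, and section 10.4.5 plans no interim analysis. Section 8.7 leaves oversight with the principal investigator, with two official reviews of adverse events, at 6 and 12 months. Participants have no formal visit between baseline and week 12. Meeting the rule also leads to a notice to the FDA, so whether it has been met should not be open to argument.

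**Working it through.** The protocol gives no derivation or operating characteristics for the threshold of three, so there is no figure to reproduce. The check sets the sections side by side.

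1. **Are the causality labels separate?** Yes. Each category in 8.2.2 has its own criteria. Definitely Related requires other contributing factors to be ruled out; Probably Related requires only that their influence be unlikely. At the other end, Not Related has its own test: "There must be an alternative, definitive etiology documented by the clinician". The text on Possibly Related also treats the top two as different outcomes: such an event "it can be flagged as requiring more information and later be upgraded to" either 'probably related' or 'definitely related'.

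2. **Which labels does 8.6 count?** One of the five, Probably Related. The sentence contains no 'at least', 'or higher' or 'definitely'.

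3. **What follows for the count?** Take three grade 3 events, each judged probably or definitely related, and let *d* be the number judged definitely related.
   - As written, the count is 3 − *d*: 3 when *d* = 0, 2 when *d* = 1, 1 when *d* = 2, and 0 when *d* = 3. The threshold of three is reached only when *d* = 0.
   - If both labels count, the total is (3 − *d*) + *d* = 3 for every *d*, and the threshold is always reached.

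   This shows how the rule works; it does not measure how often it would fail. The four values of *d* are not equally likely, and the documents give neither an event rate nor the share of events that would be labelled definite.

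4. **Does upgrading repair it?** No. An event first rated possibly related and then moved straight to definitely related, as 8.2.2 allows, never carries the one label that counts.

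5. **Severity term.** 'Grade 3' occurs twice in the text available, both times in 8.6. The 8.2.1 scale has three unnumbered levels. Severe is the third and the natural match, but no sentence makes the link, and the grading system that 8.2.1 mentions is not set out in the text available.

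6. **Do the other stopping provisions mend 8.6?** No. Section 5.8 is permissive and sets no threshold. Section 10.4.5.1 concerns enrolment, not administration. Sections 5.7.1, 6.1.8 and 7.2.6 act on individual participants. None changes which events 8.6 counts.

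**The case against.** The strongest reply is that nobody would read the rule this way. The categories run from strongest to weakest, the text speaks of upgrading, and a named level on an ordered scale is naturally taken as a minimum. The authors very probably meant probably or definitely related, and a sensible investigator would apply it so. That stands as a statement of likely intent. It does not supply the missing words in a rule whose purpose is to remove judgement.

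The second reply is that such events would not go unnoticed. Related adverse events go to the IRB within 7 days (8.4.1) and related serious ones within 3 days (8.4.2). Deaths and immediately life-threatening events go to the sponsor within 24 hours and other serious events within 72 hours, whatever their cause (8.5). Section 5.8 then offers a route to suspend the study. This also stands, and it removes most of the practical consequence. These are reporting duties and discretionary powers, though, and they leave the trigger itself unchanged.

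Third, the bar for Definitely Related is high, including satisfactory rechallenge where necessary, so few events may carry that label. This is a fair point about frequency, on which the documents give no data.

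A reader might go further and infer that 'grade 3' makes the rule unworkable. The documents do not support that. Severe is the obvious equivalent, and a definition could sit in the site monitoring plan (8.7) or the Manual of Procedures (14.3), neither of which is available here. What can be said is that the definition is missing from the text at hand.

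**Conclusion.** The point holds in a limited form. As written, 8.6 excludes definitely related events, and three of them at grade 3 would not trigger the halt. That is the wrong result for a stated safety trigger, and it rests on the text alone, with no assumed rates. The missing definition of grade 3 is a lesser matter of clarity.

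The practical risk is low: the intent is plain, discretionary stops exist in 5.8 and 10.4.5.1, no grade 3 events are predicted, and no analysis, estimand or sample size is affected. A reader might infer that participants are left unprotected, or that the rule would fail in most cases. Neither follows. The reporting and stopping provisions above remain in force, and step 3 yields no probability.

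Nor do the documents settle whether control-arm events count. Section 6.1 calls the insert the study agent and the estradiol cream the control agent, while 6.1.1 and 6.1.6 speak of both as study agents. That ambiguity is separate and is for the sponsor to resolve.

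**What to change.** Keep the sentence in 8.6 and change only the causality term, so that "Administration of study agent will be halted when three grade 3 AEs determined to be" is followed by *probably or definitely related*. The rest of the sentence stays as it is, including the words that say what is halted.

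As a secondary clarification, state in 8.6 that grade 3 means Severe or worse on the 8.2.1 scale. Severe is the top level there, so 'or worse' matters only if a numeric scale with levels above 3 is adopted.

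The correction should not add wording on which arm's events count, because that could change the scope of the rule.

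The cost is a short wording amendment, with IRB approval before it takes effect (13.2). It adds no data, visits or participants.

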8.7 Safety Oversight

It is the responsibility of the Principal Investigator to oversee the safety of the study at his/her site. This safety monitoring will include careful assessment and appropriate reporting of adverse events as noted above, as well as the construction and implementation of a site data and safety-monitoring plan. Medical monitoring will include a regular assessment of the number and type of serious adverse events. The monitoring plan includes two official review time points of all AE's noted by patients within the time frame of the study. Since the planned time frame of the study is one year, there will be one review at the 6 month mark and one at the end, 12 month mark. The outcomes of the data safety monitoring and AE's will be summarized and submitted as a progress report to the IRB with the Continuing Review Submission.

9 Clinical Monitoring

Clinical site monitoring is conducted to ensure that the rights and well-being of human subjects are protected, that the reported trial data are accurate, complete, and verifiable, and that the conduct of the trial is in compliance with the currently approved protocol/amendment(s), with GCP, and with applicable regulatory requirement(s).

- [name] will monitor the data for accuracy and completeness and the safety review will be performed by [name]. The monitoring reports will be distributed to all study investigators.
- Independent audits will not be conducted.
- Each clinical site will perform internal quality management of study conduct, data collection, documentation and completion. An individualized quality management plan will be developed to describe a site's quality management.

10 Statistical Considerations

